Once the app is installed, patients may input their procedure type and date. Patients then will select the antiplatelet medications that have been prescribed and schedule a time to receive medication reminders. The medication(s) and time of usage will be selected following the shared-decision making process between the attending physician and patient. These medication reminders may be turned off at any time on the app. Upon receiving a medication reminder, the patient must only unlock his or her phone to end the reminder message.

v. Procedure: Approximately 1 week post-screening patients will undergo their procedures. The ABQ will be administered to all patients.

vi. Follow-up plan:

1. 2-4 weeks post-procedure: This will serve as standard follow-up for all patients. The ABQ will be administered to all patients for a second time.
2. 6 months post-procedure: Standard follow-up will occur for all patients. The ABQ will be administered a third and final time.
3. Outcomes related to morbidity and mortality will be collected for all patients at 2 to 4 weeks and 6 months post-procedure.
4. Closure or termination of study: Once data collection and analysis are complete, the study will be closed.
5. **Sample Size**

We plan to enroll 68 patients undergoing stent-based aneurysm procedures (25 in the app group and 25 in the control group) at baseline.

vii. Data Safety and Monitoring: Given that the intervention is non-harmful [an app], we do not believe that a Data Safety Monitoring Plan will be necessary. The trial will go to completion.

F. Analysis

i. Statistical plan:

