All analyses will be performed according to intention to treat, where patients are analyzed as randomized. Baseline characteristics will be compared between arms using Pearson's Chi-square or Fisher's exact test for categorical variables and using 2-sample t-test or Wilcoxon rank sum test for continuous variables. The primary end point is ABQ medication compliance score. Within-arm analysis: Paired t-tests will compare ABQ scores between pre-procedure and 6 months within each arm. Primary analysis will use the 2-sample t-test to compare the ABQ score at 6 months between the two arms. These analyses will be repeated for the pre-procedure and the intermediate time point (2-4 weeks) to assess whether ABQ scores are improved with a shorter intervention period. Linear regression models will compare ABQ scores at 6 months between the 2 arms while adjusting for potential confounders such as age, sex, race/ethnicity, potential out-of-pocket expenses, and cigarette smoking status. Linear mixed models accounting for repeated measures from the same patient will be used to compare the effects of the arms (App vs. usual care) and time points while adjusting for potential confounders.

ii. Power analysis:

The study sample sizes of 25 in the App arm and 25 in the usual care arm will achieve 80% power to detect a minimum group difference of 0.80 SD between the two arms in the ABQ scores at 6 months for medication compliance with a significance level (alpha) of 0.05 using a 2-sided 2-sample t-test.

iii. Outcome measures:

Primary endpoint: medication compliance score from the Adherence Barrier Questionnaire [ABQ]. The ABQ score ranges from 14-52 and a higher score indicates that a patient faces greater barriers to adherence [7].

Assessment time points: App usage will commence when medication use is initiated 7 days prior to the procedure. The ABQ will be given 3 times: on the day of the procedure, 2-4 weeks post-procedure and 6 months post-procedure. 6-month is the primary time point.

Safety endpoints: incidence of stroke/thrombotic events/TIAs at 6 months post-treatment, as well as all-cause mortality, all-cause morbidity, rehospitalization for cerebrovascular events, peri-treatment hospitalization lasting more than 15 days, and delayed discharge from hospital.

G. Risk/Benefit Assessment**i. Risk**

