One possible risk is that participants may feel uncomfortable in sharing their health information with investigators and or research staff regarding their healthcare and demographic information. However, participation in this study is strictly voluntary and participants may leave the study at any point or refuse to answer any question. Participants also have the option to report to the project administrators any event during the study that causes any discomfort. It is important that participants know that they will not be penalized nor will their care or benefits at Montefiore be at risk if participants choose to share withhold this information.

ii. Protection against Risks

All necessary precautions will be taken to ensure that the information collected during the study is safe-guarded. Additionally, as part of the process involved in obtaining written informed consent, all participants will be reminded that their responses are confidential and that they may refuse to participate in the project or withdraw at any time without explanation, and further, that such action will in no way affect their

employment, treatment or future interactions with their supervisors or health care providers. To ensure confidentiality, all patient data will be stored in a repository accessible only with a password. We will use codes for each patient and said codes will be stored in a separate database to match with the names of the patients. We will not publish any identifying patient data.

iii. Potential Benefits to the Subjects.

We cannot and do not guarantee that participants will receive any benefits from this study. The benefit for the community at large is that the collected data will be used to establish a standard medication adherence intervention, tailor-made for cerebrovascular neurosurgery patients.

iv. Alternate procedures.

Instead of being in this study, participants have these options: They do not have to participate in this study to receive ongoing care for their current conditions. Additionally this is not a study that will diagnose or treat a disease or condition in subjects. Participants are free to choose not to participate in the study.

H. Subject Identification, Recruitment and Consent

i. Process of Consent

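### No rule covers a missing ABQ score, so the primary 6-month t-test ignores lost patients' earlier scores; the planned mixed model could use them if its 6-month contrast were named

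*Combined protocol and SAP*

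**What the plan says.** All places are in the combined protocol and SAP.

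- **F.i Statistical plan.** The primary test is: "Primary analysis will use the 2-sample t-test to compare the ABQ score at 6 months between the two arms". Analyses follow intention to treat, by randomised arm. The between-arm test is repeated separately at the two earlier visits.
- **F.i, further analysis.** "Linear mixed models accounting for repeated measures from the same patient will be used to compare the effects of the arms" and time points, with adjustment for potential confounders. No arm-by-visit term, covariance structure or 6-month contrast is stated. The nearest covariate list, given for the 6-month linear regression, is open: "adjusting for potential confounders such as age, sex, race/ethnicity, potential out-of-pocket expenses, and cigarette smoking status".
- **F.iii Outcome measures.** The ABQ is taken on the day of the procedure, at 2-4 weeks and at 6 months. Six months is the primary time point. On timing of the intervention: "App usage will commence when medication use is initiated 7 days prior to the procedure".
- **E.3.vi Follow-up plan.** At 6 months: "Standard follow-up will occur for all patients. The ABQ will be administered a third and final time".
- **G.i Risk and G.ii Protection against Risks.** "participants may leave the study at any point or refuse to answer any question", and "they may refuse to participate in the project or withdraw at any time without explanation".
- **E.3, Sample Size item.** "We plan to enroll 68 patients undergoing stent-based aneurysm procedures (25 in the app group and 25 in the control group) at baseline".

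No section says how a missing ABQ score enters any analysis. The review of files for completeness (E.3.i) is data management, not an analysis rule.

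**The concern.** A two-sample t-test at 6 months can use only patients who have a 6-month score. For a patient lost after the 2-4 week visit, two ABQ scores exist and the primary analysis uses neither. The ABQ measures barriers to adherence, and such barriers might also affect attendance. Loss related to earlier scores is therefore plausible, though nothing in the documents shows it. If high-barrier patients are lost mainly from usual care, the completers there look better than the arm as randomised, and benefit is understated. If they are lost mainly from the app arm, benefit is overstated and false claims for the app become more likely.

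The planned mixed model could use the earlier scores. As worded, however, its arm effect could be read as an average over visits, which is not the stated primary time point. If the rule is chosen after the data are seen, the choice between analyses can follow the result.

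**Working it through.** **1. The plan's own figure.** Inputs from F.ii: 25 per arm, difference 0.80 SD, two-sided alpha 0.05. Noncentrality is 0.80 × √(25/2) = 2.83. The normal approximation gives Φ(2.83 − 1.96) = 80.7%; the exact t-test gives 79.1%. The stated 80% is reproduced. With 34 per arm (68/2) exact power is 90.2%.

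**2. Complete data.** With arm, visit and arm-by-visit terms, unstructured covariance and no covariates, the model's 6-month contrast has the same estimate, SE and degrees of freedom as the t-test. The power statement then carries over.

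**3. Assumed inputs.** None of these is in the documents: 34 per arm; true 6-month benefit 0.80 SD (lower ABQ is better); normally distributed scores; correlation ρ between the 2-4 week and 6-month scores of 0.3 to 0.7; loss at 6 months only, at 10% or 26.5%. The upper rate is 1 − 50/68 = 26.5%, used only as a bound.

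**4. Random loss.** Neither method is biased. Simulated power (4,000 trials per scenario), t-test against model:
- 10% loss: 87.4% v 88.2% (ρ = 0.5) and 86.3% v 88.6% (ρ = 0.7).
- 26.5% loss: 79.0% v 82.5% and 78.0% v 84.3%.
- ρ = 0.3, about 25% loss: 81% v 81%, so no gain.

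The gain is about 0-2 points at 10% loss and 0-6 at 26.5%.

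**5. Loss in one arm that rises with the 2-4 week score.** Let z be that score in SD units within the affected arm, and P(loss | z) = 1/(1 + exp(−(a + bz))), with a set to give the stated loss L. The completers' mean is δ = ∫ z(1 − P)φ(z)dz / (1 − L). Loss depends only on z, so the completers' 6-month mean shifts by ρδ. The t-test error is therefore ρ|δ|.

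| L | b | a | δ | ρ = 0.3 | ρ = 0.5 | ρ = 0.7 |
|---|---|---|---|---|---|---|
| 10% | 0.4 | −2.26 | −0.0394 | 0.012 | 0.020 | 0.028 |
| 10% | 0.8 | −2.44 | −0.0752 | 0.023 | 0.038 | 0.053 |
| 10% | 1.2 | −2.71 | −0.1045 | 0.031 | 0.052 | 0.073 |
| 26.5% | 0.4 | −1.06 | −0.1027 | 0.031 | 0.051 | 0.072 |
| 26.5% | 0.8 | −1.16 | −0.1895 | 0.057 | 0.095 | 0.133 |
| 26.5% | 1.2 | −1.30 | −0.2550 | 0.076 | 0.127 | 0.178 |

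Simulation agrees. At 26.5%, b = 1.2 and ρ = 0.5 / 0.7, the mean t-test estimate of benefit is 0.670 / 0.622 SD with control loss (errors 0.130 / 0.178) and 0.932 / 0.974 SD with app-arm loss (errors 0.132 / 0.174). At 10% the largest simulated error is 0.875 − 0.80 = 0.075 SD.

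Type I error of the t-test is about 5-6% at 10% loss and 5-10% at 26.5%. In the same cases the model's 6-month contrast averages 0.79 to 0.81 SD, with type I error 4-6%. When both arms lose patients this way, the t-test estimate is 0.77-0.80 SD at 10% and 0.73-0.80 SD at 26.5%.

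**6. Loss driven by the unseen 6-month score** (26.5%, b = 1.2, correlation 0.5 or higher). The t-test gives about 0.55 SD (control loss) or 1.05 SD (app-arm loss); the model gives 0.61-0.68 or 0.92-0.99 SD. The model is nearer the true 0.80 SD but still biased.

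**7. t-test after multiple imputation by arm.** Under random loss and loss tied to earlier scores, its estimates match the model's. Its power under random loss is below the plain t-test in 6 of 12 cases. For example, with 25 per arm and 20% loss it is 67.1% v 68.5% at ρ = 0.5, although 72.4% v 68.6% at ρ = 0.7. Some of these gaps are within simulation error.

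**The case against.** The strongest reply is that the defect is a missing rule, not a wrong test. The t-test is the analysis the trial is powered on, and the mixed model would be reported anyway. The 6-month ABQ falls at a visit planned as standard follow-up for everyone, and the withdrawal wording reads as generic consent language, so loss may be small. At 10% loss the worst error is about 0.08 SD, one tenth of the 0.80 SD design difference, and type I error is nearly nominal. The larger figures need strong selection: at 26.5% loss and slope 1.2, loss is 1/(1 + e^2.5) = 8% at one SD below the mean and 1/(1 + e^0.1) = 47.5% at one SD above. Patients who leave before 2-4 weeks give the model less to recover.

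Most of this stands. It limits the size, and it makes a primary mixed model a good option rather than the only one. It does not supply a missing-score rule or a 6-month contrast.

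Three stronger readings are tempting and unsupported:
- **That the t-test contradicts intention to treat.** The plan's wording concerns the arm in which patients are analysed, not absent scores.
- **That 68 against 25 + 25 is a 26.5% dropout allowance.** Both figures are given at baseline and no dropout rate is stated; reconciling them is a separate matter.
- **That the mixed model will test an average over visits.** The text leaves this open; it does not say so.

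**Conclusion.** The point holds as a cheap improvement that should be made, not as a flaw that invalidates the trial. The gap itself is certain from the text: there is no missing-score rule, the primary test uses only patients with a 6-month score, and the planned model does not state that it targets 6 months. The consequence is conditional on loss, correlation, score distribution and mechanism, none of which the documents give.

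Under the assumptions in the working, the main gain is protection against bias when loss depends on earlier scores; the gain in power is small and can be nil. A reader might infer that the primary result will be biased, or that the mixed model cures missing data. Neither follows. Complete or randomly missing data leave the t-test unbiased, and the model relies on missing at random.

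**What to change.** In F.i, make primary the 6-month arm difference from the already planned linear mixed model of all available ABQ scores. Specify arm, visit and arm-by-visit terms, unstructured within-patient covariance, REML, Kenward-Roger degrees of freedom and no covariates. Treat the day-of-procedure ABQ as an outcome with its own mean in each arm: app use starts 7 days earlier, so that score is not a pre-intervention baseline. Keep the 6-month t-test as a sensitivity analysis, report missing scores by arm and visit, and add one imputation analysis in which imputed 6-month scores are shifted over a range of values.

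If the sponsor prefers the t-test as primary, name the 6-month contrast of this model as the key supporting analysis. A t-test after multiple imputation by arm also reduces the bias, but in arms this small it may recover no power or lose a little.

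Cost: SAP wording only, with no new visits, data or patients. The downside is reliance on missing at random, and patients with no ABQ at all still contribute nothing to the model.

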Flow-diverter devices (FDDs) such as the Pipeline Embolization Device (PED) are next-generation stents that are placed at neck of the aneurysm in order to significantly diminish blood flow into the aneurysm, which ultimately results in aneurysm thrombosis. Another method used to treat aneurysms is stent-assisted coiling. These procedures, however, bring with them risk of stroke and thrombosis/stenosis and thus require antiplatelet medications both prior to and post treatment.

Dual antiplatelet therapy [DAPT] in the form of aspirin and clopidogrel, a thienopyridine, is most common. A survey by Faught *et al.* found that among neurointerventionalists practicing in America, the most commonly prescribed antiplatelet therapy was aspirin 325 mg and clopidogrel 75 mg daily for seven days or five days prior to the procedure. Maintenance therapy following FDD placement is commonplace, with only 15.6% and 30.2% of practitioners refraining following intracranial and cervical stent placement, respectively. Aspirin 325 mg daily for life and clopidogrel 75 mg daily for three months was the most common maintenance therapy aside from the choice “other” [2].

Discontinuation of antiplatelet medication has been found to be associated with thrombotic events. A review article by Briganti *et al.* reported a mean incidence of 3.8% for parent artery thrombosis or 50 percent or greater stenosis during the FDD

implantation procedure in 12 studies. An occlusion or stenosis rate of 6.8% by the time of angiographic follow-up was found in 16 studies. Mean angiographic follow-up was nine months, with a range of three to thirty months. The authors note that these later findings were frequently incidental and were associated with termination of clopidogrel [1]. This association has also been found in the case of stent-assisted coiling. Mocco *et al.* found that seven out of 213 patients who received stent-assisted coiling of aneurysms developed delayed thrombotic events. Furthermore, the authors reported that prior to these events, the patients were not taking DAPT, which consisted of aspirin and clopidogrel [6].

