Text-based reminders have been shown to decrease medication noncompliance. Park *et al.* explored the impact of text messaging on antiplatelet and statin adherence among patients who had suffered an MI or received percutaneous coronary intervention [PCI]. The mean age was 59.2 years. Text medication reminders required acknowledgement of receipt. Patients who received text messages took a significantly greater percentage of correct doses taken [$p=0.02$] and percentage of prescribed doses taken [$p=0.01$] compared to those who did not receive such reminders. No significant difference in percentages of doses of statins taken was found [9]. Foreman *et al.* found that patients who received text message reminders regarding chronic oral medications were significantly more likely to take the appropriate dosages. Regarding antidiabetes medications, the text message cohort had a mean compliance rate of 0.91 compared to a rate of 0.82 for the control group ($p=0.029$). A significant increase in β -blocker compliance was also found,

with a mean compliance rate of 0.88 for the text message cohort opposed to a 0.71 rate for the control group ($p=0.006$) [3].

The advent of an antiplatelet reminder app for FDDs and stent-assisted coiling holds the possibility of not only improving medication compliance but also of decreasing the incidence of thrombotic events following said procedures. The effectiveness of this app may be assessed via a prospective cohort study. We would like to develop a tailored standardized intervention for endovascular patients receiving DAPT that extends beyond the traditional teach-back method and follow-up evaluation.

3. Research Question:

To test the efficacy of a medication reminder app regarding DAPT compliance, with compliance estimated by patients' ABQ scores. The free app is called Endovascular Neurosurgery and is available on the Apple App Store. It was developed by [name] and does not collect user data. The only data inputted into the app are the patient's procedure date and the antiplatelet medications the patient has been prescribed. The app does not possess patient data. Montefiore IT stated that it does not monitor apps that patients download onto their own devices. Both groups will receive the same standard of care, including any information on the risks of DAPT nonadherence.

C. Research Population or Study Sample Selection

1. Study Setting:

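### Bleeding is not prespecified as a separate safety endpoint, although the app aims to increase intake of two antiplatelet drugs

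*Combined protocol and SAP*

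**What the plan says.** Section F.iii (Outcome measures) states: "Safety endpoints: incidence of stroke/thrombotic events/TIAs at 6 months post-treatment, as well as all-cause mortality, all-cause morbidity, rehospitalization for cerebrovascular events". It closes the list with "peri-treatment hospitalization lasting more than 15 days, and delayed discharge from hospital". Stroke and morbidity are not defined, and section F.i (Statistical plan) specifies no analysis for any safety endpoint.

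On collection, section E.3.vi (Follow-up plan, item 3) says: "Outcomes related to morbidity and mortality will be collected for all patients at 2 to 4 weeks and 6 months post-procedure".

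On the purpose of the app, section B.2 (Background) says it "holds the possibility of not only improving medication compliance but also of decreasing the incidence of thrombotic events following said procedures". The same section describes the treatment: "Dual antiplatelet therapy [DAPT] in the form of aspirin and clopidogrel, a thienopyridine, is most common".

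On harm, section E.3.vii (Data Safety and Monitoring) says: "Given that the intervention is non-harmful [an app], we do not believe that a Data Safety Monitoring Plan will be necessary". Section G.i (Risk) begins: "One possible risk is that participants may feel uncomfortable in sharing their health information with investigators and or research staff". It names no risk from taking more of the prescribed drugs.

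**The concern.** If the app works, patients take more of two drugs that reduce clotting. Bleeding is the direct counterpart of the benefit sought, and the protocol already accepts that the therapy carries risk, because contraindications to it are an exclusion (section D.2). Yet the safety list names thrombotic events and does not name bleeding.

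The stake is the balance of the safety report. Section G.iii says the data will be used to establish a standard adherence intervention for these patients. A reader of the results would see a thrombotic count by arm, but the plan requires no matching bleeding count. If stroke is counted without regard to type, one fewer ischaemic stroke and one more haemorrhagic stroke in the app arm would net to no difference (−1 + 1 = 0), and the two effects would be hidden.

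**Working it through.** **1. The plan's only power figure.** Section F.ii refers to "The study sample sizes of 25 in the App arm and 25 in the usual care arm" and states 80% power for a 0.80 SD difference in 6-month ABQ score, two-sided alpha 0.05. Normal approximation: Φ(0.80 × √(25/2) − 1.96) = Φ(2.83 − 1.96) = Φ(0.87) ≈ 80.7%. The exact noncentral t gives 79.1%. The figure reproduces, but it concerns the ABQ score. No power or precision is stated for any safety endpoint.

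**2. Where a bleed could be recorded under the present list.**
- Extracranial bleed: all-cause morbidity (undefined), or mortality if fatal. It falls outside cerebrovascular rehospitalisation.
- Intracranial bleed: the same categories, and possibly stroke (type not stated) or cerebrovascular rehospitalisation.
- Peri-procedural bleed: also a stay over 15 days or a delayed discharge, if it prolongs admission.

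None of these categories requires that bleeding be asked about, graded or tabulated by arm.

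**3. Arm size.** Section C.3 plans 68 patients at 1:1, so 68/2 = 34 per arm. Section F.ii and the Sample Size item in section E.3.vi give 25 per arm. Both are used below.

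**4. Chance of at least one bleed in an arm**, 1 − (1 − p)^n. The documents give no bleeding rate, so p is an assumption.

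| Assumed 6-month rate | n = 34 | n = 25 |
|---|---|---|
| 1% | 1 − 0.99^34 = 29% | 1 − 0.99^25 = 22% |
| 3% | 1 − 0.97^34 = 64% | 1 − 0.97^25 = 53% |
| 5% | 1 − 0.95^34 = 83% | 1 − 0.95^25 = 72% |

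**5. What zero bleeds in an arm would allow the trial to state.** One-sided 95% upper bound: 1 − 0.05^(1/34) = 8.4%, or 1 − 0.05^(1/25) = 11.3%. Upper limit of the two-sided 95% interval: 1 − 0.025^(1/34) = 10.3%, or 1 − 0.025^(1/25) = 13.7%.

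**6. What naming bleeding would not achieve.** Power of the two-sided Fisher exact test at 0.05, and the size needed for 80% power, at assumed rates:

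| Rates by arm | Power, 34 per arm | Power, 25 per arm | n per arm for 80% |
|---|---|---|---|
| 1% vs 2% | <0.1% | <0.1% | 2319 |
| 2% vs 5% | 0.3% | 0.1% | 588 |
| 5% vs 10% | 2.8% | 1.3% | 435 |
| 10% vs 20% | 12.2% | 8.6% | 199 |

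The last column uses a normal-approximation formula for two proportions. With no bleeds in one arm, the other would need at least 6 for p ≤ 0.05: 6/34 = 17.6%, or 6/25 = 24%.

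**The case against.** The strongest reply is that bleeds are not shut out. All-cause mortality and all-cause morbidity are listed safety endpoints, and morbidity and mortality outcomes are collected for every patient at both follow-ups. The app only reminds patients about drugs already prescribed, both arms receive the same standard of care, and the primary endpoint is a questionnaire score. The absence of a safety analysis applies to the whole list and is not special to bleeding. All of this stands, and it limits the weight of the point.

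It also rules out several stronger readings that a reader might infer:

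- *The trial cannot record the harm its intervention might cause.* It can, through the categories in step 2 of the working. What is missing is a definition and a separate count.
- *Every specific event listed is one the app is hoped to reduce.* Section B.2 expresses that hope for thrombotic events only. Stroke is not limited to ischaemic stroke, and the two length-of-stay items are neutral in direction.
- *No bleed would be reported separately.* The documents do not say how morbidity will be itemised, and the case-report form and appendices were not supplied. Silence supports saying that separate reporting is not specified, and no more. The consent pages were also removed and may mention bleeding, but that would not make it an endpoint in section F.iii.
- *Naming bleeding would let the trial show an excess.* It would not, as step 6 shows. Size limits the listed thrombotic events in the same way.

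What the reply does not answer is that nothing in the plan requires bleeding to be asked about or reported by arm, or haemorrhagic stroke to be kept apart from thrombotic events.

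**Conclusion.** The point holds as a gap in prespecification and reporting. Bleeding has no endpoint of its own, a bleed could appear only inside undefined or non-specific categories, and pooling by stroke type could conceal opposite effects. The primary ABQ analysis is unaffected.

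At least one bleed in an arm is plausible: 29% to 83% with 34 patients, or 22% to 72% with 25, over assumed 6-month rates of 1% to 5%. These figures rest on the assumed rates, on independence between patients and on complete follow-up of the stated arm size. A between-arm difference cannot be shown reliably at this size, since power is at most 12.2% even for an assumed 10% vs 20%. The gain is therefore a balanced descriptive record. This is a cheap improvement that should be made, and it does not affect the validity of the primary result.

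**What to change.** In section F.iii:
- Add bleeding events as a safety endpoint, intracranial and extracranial, with those needing hospitalisation or transfusion counted separately.
- Report haemorrhagic stroke separately from ischaemic stroke and TIA.
- List rehospitalisation for bleeding as its own item. Do not merge it into cerebrovascular rehospitalisation, because a merged item would again let opposite effects cancel.

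In section E.3.vi, item 3, name bleeding among the outcomes collected at the 2-4 week and 6-month visits. In section F.i, state that these endpoints will be reported as counts with exact confidence intervals by arm, descriptively and without a claim of comparative power.

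The cost is a few case-report fields at visits already planned and a little more data entry. Sample size, treatment and the primary analysis do not change.
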